### 10.4. Laboratory Evaluations

Clinical laboratory tests are performed at Screening, Baseline, Week 8, Week 16, Follow-up Visit, and Early Termination Visit. All laboratory values will be reported in SI units.

For statistical and graphical summaries of the laboratory tests, values below or above the limit of detection (e.g. '< 3' or '>500') are substituted with the lower limit of detection minus 1% for values below the lower limit and are substituted with the upper limit of detection plus 1% for values above the upper limit (e.g. '< 3' is substituted by '2.97', '> 500' is substituted by '505'). In data listings, the values are shown including the < or > sign.

Results from the central laboratory (hematology, blood chemistry and urinalysis) will be summarized by treatment group and visit using descriptive statistics, including observed values and change from baseline values (for numeric laboratory parameters), distribution of categories (for categorical laboratory parameters). By visit summaries will be performed at all visits (scheduled and ET visits) and for the last post-baseline results during treatment period. Last-post baseline results will include unscheduled visits in the derivation.

In addition, the number and percentage of subjects who met criteria of Potentially Clinically Significant Values (PCSV) will be summarized by treatment group and by visit. Criteria for PCSV are included in Section 20.2.

Shift tables from baseline will be generated by treatment group using the reference ranges at each visit, last post-baseline during treatment period, the worst post-baseline. Hematology, chemistry and applicable urinalysis results will be classified as low (L), normal (N), and high (H) by the laboratory parameter's normal range. Worst post-baseline value is defined the value farthest from the reference range (lower and higher limit). If all post-baseline values are "Normal", the subject is classified as Normal. If any post-baseline value is "Abnormal" ("High" or "Low"), select the farthest one from Lower or Higher limit of reference range.

Distribution of Aspartate Aminotransferase (AST), Alanine Aminotransferase (ALT), Alkaline Phosphatase (ALP), Total bilirubin and Creatinine Phosphokinase (CPK) will be displayed graphically as boxplot by treatment group for each scheduled visit and the maximum post-baseline values.

Listings for laboratory test satisfying PCSV criteria and all laboratory tests (hematology, blood chemistry, urinalysis, pregnancy test, virology, tuberculosis test) will be provided.

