13.3 Vital Signs

Vital signs will be evaluated at the screening visit and at each subsequent visit according to [Table 4](#). Vital signs will include pulse rate, systolic and diastolic blood pressure (after the subject has been sitting for at least 5 minutes), and body temperature. All abnormal values at the screening visit identified as clinically significant by the investigator will be recorded in the medical history form. Any clinically significant changes from the screening visit will be recorded as an AE.

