#### 6.4. Visit Windows

Efficacy by-visit summaries will use the analysis visit. Unscheduled and early termination visits will be windowed based on the following analysis visit window which is based on study day. If multiple measurements are taken within the same window, the one taken closest to the target study day will be

used for the analysis. If there are multiple measurements with same difference from target day, the later assessment should be used for the analysis.

Analysis Visit	Target Study Day (relative to first treatment date)	Analysis Visit Window
Baseline	1	<=1
Week 4	29	2 to 42
Week 8	57	43 to 71
Week 12	85	72 to 99
Week 16	113	100 to 141
Week 24 Follow-up	169	> 141

Safety and pharmacokinetics data will not be windowed for by-visit summary. i.e., scheduled visit (including Early Termination visit) data will be used for analysis. For clinical laboratory assessments, if repeated measurements are taken for either time point (scheduled visit), then the last measurement will be used for the value for that time point.

Daily diary efficacy data (CCI ) will be classified into analysis visits as follows. Analysis Visit Target Study Day of Analysis Visit (relative to first treatment date) Baseline 1 Week 1 8 Week 2 15 22 Week 3 Week 4 29 Week 5 36 Week 6 43 Week 7 50 57 Week 8 Week 9 64 Week 10 71 Week 11 78 Week 12 85 92 Week 13 Week 14 99 Week 15 106 Week 16\* 113

These analysis visits will be used in the calculations for all week-based parameters collected on subject's diary data. Other non-diary data, such as, vital signs, body weight, clinical laboratory assessments, respiratory assessment/PEF, will be analyzed according to actual scheduled visits.

Unscheduled labs will be included in listings and considered in the derivation of last, worst post-baseline values, but not summaries of the data by visit.

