#### 10.5. Vital Signs, Weight and Height

Weight, Height and Vital signs including systolic blood pressure, diastolic blood pressure, pulse rate and temperature will be summarized using descriptive statistics by treatment group and visit, including observed values and change from baseline values. By visit summaries will be performed at all visits (scheduled and ET visits) and for the last post-baseline results during treatment period. Last-post baseline results will include unscheduled visits in the derivation.

In addition, the number and percentage of subjects who met criteria of Potentially Clinically Significant Values (PCSV) will be summarized by treatment group and by visit. Criteria for PCSV are included in Section 20.2.

Shift tables from baseline will be generated by treatment group using the reference ranges at each visit, last post-baseline during treatment period, the worst post-baseline. Weight, Height and Vital signs results will be classified as normal, abnormal CS (clinically significant), and abnormal NCS (not clinically significant). Worst post-baseline value is defined the value farthest from the reference range (lower and higher limit). If all post-baseline values are "Normal", the subject is classified as Normal. If any post-baseline value is "Abnormal" ("High" or "Low"), select the farthest one from Lower or Higher limit of reference range.

Vital signs data and data satisfying PCSV criteria will also be listed.

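### The worst post-baseline shift keeps one value per subject by an undefined distance, so it can drop a low or high laboratory result, or report a not clinically significant vital sign as worst for a subject who had a clinically significant one

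*SAP*

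**What the plan says.** **Laboratory values (SAP 10.4).** The categories are set out as "Hematology, chemistry and applicable urinalysis results will be classified as low (L), normal (N), and high (H) by the laboratory parameter's normal range". Shift tables from baseline are planned "using the reference ranges at each visit, last post-baseline during treatment period, the worst post-baseline". The worst value is defined as "Worst post-baseline value is defined the value farthest from the reference range (lower and higher limit"). If any post-baseline value is abnormal, the instruction, which SAP 10.4 and SAP 10.5 give in the same words, is to "select the farthest one from Lower or Higher limit of reference range".

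**Vital signs, weight and height (SAP 10.5).** The definition and selection sentences are repeated, but the categories differ: "Weight, Height and Vital signs results will be classified as normal, abnormal CS (clinically significant), and abnormal NCS (not clinically significant"). I abbreviate these as CS and NCS.

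**Unscheduled results (SAP 6.4).** Unscheduled labs go into listings and are "considered in the derivation of last, worst post-baseline values, but not summaries of the data by visit". SAP 10.4 and 10.5 also put unscheduled visits into the last post-baseline result. SAP 10.5 does not say whether unscheduled vital signs enter the worst value.

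**Other outputs.** For labs and vital signs alike, counts of "Potentially Clinically Significant Values (PCSV) will be summarized by treatment group and by visit" are planned, with listings of all results and of those meeting the PCSV criteria. SAP 10.4 adds boxplots that include the maximum post-baseline value for AST, ALT, ALP, total bilirubin and CPK.

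**The concern.** A worst-value shift table exists to show the most extreme abnormality each subject reached at any time. Two features of the rule can stop it doing so.

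- For labs, low and high are different safety signals, but they compete for one cell. A subject who was low once and high once is recorded as only one of these.
- For vital signs, the table reports clinical significance but the selection ignores it. A subject with a CS value can be tabulated as NCS.

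The word farthest is also left without a metric, so two programmers could follow the SAP and produce different tables. What is at stake is the accuracy of one panel in the laboratory and vital-sign shift tables. That matters most for unscheduled labs, which have few other routes into a summary.

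**Working it through.** There is no stated figure to reproduce; the point concerns a derivation rule. All reference ranges and values below are assumed for illustration.

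**1. Is it one value or two?** The parenthesis naming both limits could be read as one worst value in each direction. The selection sentence rules this out, because it picks the farthest one from either limit. There is also no combined low-and-high category, so each subject has one category per parameter.

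**2. Labs under two plausible metrics.** Absolute distance is (lower limit - value) for a low result and (value - upper limit) for a high one. Relative distance divides this by the limit that was breached.

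| Assumed range | Values | Absolute, low vs high | Selected | Relative, low vs high | Selected |
|---|---|---|---|---|---|
| Platelets 150-400 | 60, 495 | 150-60 = 90 vs 495-400 = 95 | High | 90/150 = 60% vs 95/400 = 24% | Low |
| Neutrophils 1.8-7.7 | 0.6, 9.0 | 1.8-0.6 = 1.2 vs 9.0-7.7 = 1.3 | High | 1.2/1.8 = 67% vs 1.3/7.7 = 17% | Low |

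Under either metric one abnormality is lost from the worst shift. The metric decides which one.

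**3. Vital signs.** Assume a range of 90-140, a value of 82 judged CS and a value of 152 judged NCS. The absolute distances are 90-82 = 8 and 152-140 = 12, so the rule reports NCS. Relative distances are 8/90 = 8.9% and 12/140 = 8.6%, which narrowly reverses the choice. The defect does not need opposite directions, though. If two values lie on the same side of the range, and the nearer is judged CS and the farther NCS, both metrics select the NCS value.

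This requires that CS is not simply a function of distance. Protocol 13.3 speaks of "All abnormal values at the screening visit identified as clinically significant by the investigator", which ties the flag to investigator judgement at screening. Carrying that over to later visits is an inference.

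**4. Where a displaced laboratory value still appears.**

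- Scheduled value: by-visit shift table, by-visit PCSV count and listings.
- Unscheduled value: listings. It reaches the last post-baseline summaries only if it is the last value in the treatment period, and the adverse event tables only if it is reported as an event. A high value of one of the five plotted analytes might also show in the maximum boxplot, if unscheduled values count there, which the SAP does not say. No output summarises minimum values.

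**5. How often?** The documents give nothing from which to compute this. As an illustration only, I took independent normal draws, limits at ±1.96, 3 or 4 post-baseline values and a standard deviation of 1.0 to 1.5. The share of subjects with any low value who lose it from the worst shift under absolute distance is then 2.5% (3 values, SD 1.0) to 13.6% (4 values, SD 1.5). As a share of all subjects this is 0.0248 × 0.0735 = 0.2% to 0.1358 × 0.3297 = 4.5%. Repeated values in one subject are usually positively correlated, which makes opposite excursions rarer, so these are not estimates for this trial.

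**The case against.** The strongest reply is that little is really hidden. Scheduled values appear in the by-visit shifts and PCSV counts, and every laboratory and vital-sign result is listed. Protocol 13.2 has clinically significant out-of-range labs that are new or worsened since screening reported as adverse events, and Protocol 13.3 does the same for clinically significant changes in vital signs. These reach the tables by system organ class and preferred term in SAP 10.3. Labs are scheduled after baseline only at Week 8, Week 16, follow-up and early termination, so opposite excursions in one analyte should be uncommon. All of this stands, and it limits the size of the point.

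It does not remove the point. An adverse event table is not a laboratory shift table, and an out-of-range value not judged clinically significant need not become an event. None of these outputs corrects a worst category that is wrong.

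Two stronger readings are tempting and should not be drawn.

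- **That high values systematically mask low ones.** This needs absolute distance, which the SAP does not specify, and both laboratory examples reverse under relative distance. Even with absolute distance, the floor at zero matters only where the lower limit is small compared with the excursions that occur, and a low value can equally displace a high one.
- **That clinically significant vital signs seen off schedule vanish from the worst shift.** SAP 6.4 sends unscheduled labs to the worst-value derivation and does not mention vital signs. SAP 10.5 brings unscheduled visits into the last post-baseline result only.

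**Conclusion.** The point holds as a minor safety-reporting error. On the SAP's own wording, the worst shift can show only one of two opposite laboratory abnormalities, with the choice resting on an undefined metric. It can also report NCS as worst for a subject with a CS vital sign. The largest gap is an unscheduled laboratory value that is displaced: unless it is also the last post-baseline value or is reported as an adverse event, it is in general left to the listings.

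The laboratory conclusion rests on the text alone; the examples only illustrate it. The vital-sign conclusion also assumes that post-baseline clinical significance is judged and not computed from distance. The number of subjects affected is unknown. A reader might infer that the safety objective is compromised, but by-visit tables, PCSV counts, listings and adverse event reporting do not support that. The primary vaccine-response analysis is untouched.

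**What to change.** - **SAP 10.4:** replace the single worst shift with two per parameter, baseline to lowest and baseline to highest post-baseline value, both including unscheduled labs. A subject with both abnormalities is then counted in each, and no distance metric is needed. Apply this to Tables 14.3.4.1.1.2, 14.3.4.1.2.2 and 14.3.4.1.3.2 (numeric urinalysis parameters only).
- **SAP 10.5:** define worst by category, CS above NCS above Normal, and remove the High/Low selection wording, which does not match this table's categories. State whether unscheduled vital signs are included. Apply this to Table 14.3.4.2.2.

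The cost is a wording change and one extra panel in each laboratory shift table, with a footnote that a subject may appear as abnormal in both panels. No new data are needed.

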#### 10.5. Vital Signs, Weight and Height

Weight, Height and Vital signs including systolic blood pressure, diastolic blood pressure, pulse rate and temperature will be summarized using descriptive statistics by treatment group and visit, including observed values and change from baseline values. By visit summaries will be performed at all visits (scheduled and ET visits) and for the last post-baseline results during treatment period. Last-post baseline results will include unscheduled visits in the derivation.

In addition, the number and percentage of subjects who met criteria of Potentially Clinically Significant Values (PCSV) will be summarized by treatment group and by visit. Criteria for PCSV are included in Section 20.2.

Shift tables from baseline will be generated by treatment group using the reference ranges at each visit, last post-baseline during treatment period, the worst post-baseline. Weight, Height and Vital signs results will be classified as normal, abnormal CS (clinically significant), and abnormal NCS (not clinically significant). Worst post-baseline value is defined the value farthest from the reference range (lower and higher limit). If all post-baseline values are "Normal", the subject is classified as Normal. If any post-baseline value is "Abnormal" ("High" or "Low"), select the farthest one from Lower or Higher limit of reference range.

Vital signs data and data satisfying PCSV criteria will also be listed.

#### 10.6. ECG

A standard 12-lead ECG will be performed at Screening, Week 16, and Early Termination Visit. ECGs will be performed in the supine position. Subjects will be monitored for potentially clinically significant ECG results. Tests with abnormal results that are deemed clinically significant will be repeated to ensure reproducibility of the abnormality.

The overall ECG interpretations will be collected as "Normal", "Abnormal, not clinically significant" and "Abnormal, clinically significant". Summary of overall interpretation will be tabulated by treatment group and visit.

Listings for all ECG data will be provided.

### 10.7. Physical Examination

Complete physical examination (PE) will be performed at the Screening, Week 8, Week 16, and Early Termination Visit. A complete physical examination will include assessments of the head, ears, eyes, nose, throat, neck (including thyroid), skin/integumentary system, cardiovascular system, respiratory system (for additional respiratory assessments), gastrointestinal system, musculoskeletal system, lymph nodes, and nervous system.

The PE results will be categorized as "Normal", "Abnormal, not clinically significant" and "Abnormal, clinically significant". Summary table of PE results will be provided by treatment group, visit and body system. Listing will also be provided.

## 10.8. Respiratory Assessments

All data will be listed. A separate listing will be provided for subject with a drop by >= 15% from Baseline for either PEF or ACT.

#### **10.8.1.** Asthma Control Test (ACT)

Subjects with a medical history of asthma will take the ACT at all visits according to Table 1. Subjects with a new (de novo) diagnosis of asthma will take the ACT beginning at the visit the diagnosis was first confirmed and at all subsequent study visits thereafter. Subjects with an ACT score ≤ 19 will be referred to the physician managing their asthma.

The ACT is an assessment to determine if a subject's asthma symptoms are well controlled. The ACT is designed for adults and adolescents 12 years or older and is composed of 5 questions. For each question, the subject will choose the best answer out of 5 possible answers. The test provides a

numerical score ranging from 5 to 25 to assess asthma control; a higher score indicates better asthma control while a score of 19 or less indicates the subject's asthma may not be under control.

Results from ACT test will be summarized by treatment group and visit using descriptive statistics, including observed values and change from baseline values.

Number and frequency of subjects with ACT score ≤ 19 will be summarized by visit and by treatment group.

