13.4 Height and Weight

Height and weight will be measured, according to [Table 4](#).

Subjects must be at least 30 kg at both screening and baseline visits in order to be enrolled into this clinical study.

After the screening visit, additional height assessments will only be conducted for adolescent subjects (aged 12 to 17).

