#### 6.2. Key Definitions

#### 6.2.1. Baseline

Unless otherwise stated, the baseline value for any variable will be the last non-missing value taken prior to the receipt of study treatment at the Baseline visit (Day 1). The receipt of study treatment is defined as the 1st injection of study drug if it exists. Otherwise, baseline is defined as the last value taken prior to the randomization.

For diary data (CCI), the baseline values will be derived from data collected during the 7 days prior to the first administration of study drug, if it exists. Otherwise, the data collected during 7 days prior to randomization will be used. Baseline score will be the weekly prorated average of non-missing subject diary scores reported during the 7 days. A minimum of 4 daily scores out of the 7 days is required to calculate the weekly prorated average score.

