#### **10.8.3.** Peak Expiratory Flow (PEF)

PEF measurements will be performed for all subjects at Screening, Baseline, Week 8, Week 16, Follow-up Visit, and Early Termination Visit. For subjects reporting a medical history of asthma, PEF measurements will be performed at all visits during the clinical study (ie, PEF testing at Visit 3 and 5 will occur in asthmatic subjects only). For subjects diagnosed with de novo asthma, PEF measurements will be performed at all visits starting with the visit in which the diagnosis was confirmed.

Results from PEF testing [actual PEF rate (L/min) and/or actual PEF rate of the predicated value (%)] will be summarized by treatment group and visit using descriptive statistics, including observed values and change from baseline values.

Number and frequency of subjects with abnormal PEF (actual PEF < 80% of the predictive value) will be summarized by visit, treatment group.

Statistical Analysis Plan
Sponsor: Galderma S.A./Galderma R&D, LLC; Protocol No.: RD.06.SPR.118380 V4.0, 06Jul2022

All PK parameters will be listed by subject.

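### Observed by-visit ACT and PEF summaries, and their threshold counts, describe different groups of subjects at different visits (SAP 10.8.1 and 10.8.3)

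*SAP*

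**What the plan says.** **ACT (SAP 10.8.1).** The starting group is defined by history: "Subjects with a medical history of asthma will take the ACT at all visits according to Table 1". New cases are added as they arise: "Subjects with a new (de novo) diagnosis of asthma will take the ACT beginning at the visit the diagnosis was first confirmed". Protocol 13.6.1 agrees. The planned output is "Results from ACT test will be summarized by treatment group and visit using descriptive statistics, including observed values and change from baseline values", plus the number with ACT ≤ 19 by visit and arm.

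**Baseline (SAP 6.2.1).** "Unless otherwise stated, the baseline value for any variable will be the last non-missing value taken prior to the receipt of study treatment". A subject first given the ACT at an on-study diagnosis has no such value.

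**PEF (SAP 10.8.3).** All subjects are measured at Screening, Baseline, Weeks 8 and 16, Follow-up and Early Termination. In between, "PEF testing at Visit 3 and 5 will occur in asthmatic subjects only". Subjects with de novo asthma are measured at every visit from diagnosis onward. Observed values, change from baseline and the number below 80% of predicted are summarised by arm and visit.

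**Listing (SAP 10.8).** "A separate listing will be provided for subject with a drop by >= 15% from Baseline for either PEF or ACT".

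**Tables (SAP 17).** There is one ACT summary, one ACT ≤ 19 summary, one PEF summary and one PEF < 80% summary, all on the SAF. No title mentions asthma history. The subgroups in SAP 6.6 apply to vaccine response and selected efficacy endpoints, not to safety.

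**Height.** SAP 10.5 summarises height by visit, yet Protocol 13.4 states that after screening "additional height assessments will only be conducted for adolescent subjects".

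**The concern.** A by-visit table invites the reader to follow a row across time. That works only if the row describes the same people at each visit, or if the table says who is in it.

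For PEF, the row moves from everyone to asthmatic subjects and back. Asthmatic subjects may well have lower PEF, so the observed mean can fall and recover with nobody changing.

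For ACT, the starting group is selected for good control, because Protocol 5.3.1 says subjects with ACT ≤ 19 are excluded. Late entrants pass no such filter and join when their asthma has just been recognised. They enter the observed mean and the ≤ 19 count, but not change from baseline. The two parts of the same table then describe different sets of subjects.

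Protocol 5.3.1 names newly diagnosed or worsening asthma as an important potential risk. Diagnosis happens after randomisation. If treatment affects it, a lower observed ACT mean on one arm could be read as existing asthma getting worse when it reflects new cases entering.

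**Working it through.** The documents state no figure for this point, so there is nothing to reproduce. The check holds every subject's value constant and changes only who is measured.

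**Input from the documents:** 123 subjects per arm (SAP 3.5).

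**Assumed inputs:** asthma history in 20% to 50% of an arm (25 to 62 of 123); ACT mean 23 in that group with nobody at ≤ 19, in line with the entry exclusion; 0 to 5 new cases per arm, each scoring 14 to 19; PEF 100% of predicted in non-asthmatic subjects and 5 to 15 points lower in asthmatic subjects.

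**1. Which visits.** SAP 10.8.3 names the visits at which all subjects are tested. Weeks 4 and 12 are the scheduled treatment visits left over, so Visits 3 and 5 are Weeks 4 and 12. The schedule table is not visible in the public text, so this is by elimination.

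**2. PEF mean.** With *a* asthmatic subjects of 123 and gap *d*:
- All-subject visit: [*a*(100 − *d*) + (123 − *a*)·100]/123
- Visits 3 and 5: 100 − *d*
- Shift: −*d*(1 − *a*/123)

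For *a* = 25 and *d* = 10, the all-subject mean is (25·90 + 98·100)/123 = 98.0. Visits 3 and 5 show 90.0, and the next all-subject visit returns to 98.0. The smallest shift is 5·(61/123) = 2.5 points (*a* = 62, *d* = 5). The largest is 15·(98/123) = 12.0 points (*a* = 25, *d* = 15).

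**3. PEF < 80% at constant risk.** Take *a* = 43, an on-study risk of 10% in asthmatic subjects and 5% in others.
- All-subject visits: (4.3 + 4.0)/123 = 6.7%
- Visits 3 and 5, SAF denominator: 4.3/123 = 3.5%
- Visits 3 and 5, those measured: 4.3/43 = 10.0%

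The SAF denominator is the default in SAP 15.2.5.2. Choosing the other one reverses the direction of the artefact but does not remove it.

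**4. ACT observed mean.** With *k* history subjects at 23 and *m* new cases at score *s*, the mean is (23*k* + *sm*)/(*k* + *m*).
- *k* = 25, *m* = 3, *s* = 17: (575 + 51)/28 = 22.36, a fall of 0.64
- Smallest: *k* = 62, *m* = 1, *s* = 19: (1426 + 19)/63 = 22.94, a fall of 0.06
- Largest: *k* = 25, *m* = 5, *s* = 14: (575 + 70)/30 = 21.50, a fall of 1.50
- *m* = 0: no shift

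**5. ACT ≤ 19.** This rises from 0% to between 1/123 = 0.8% and 5/123 = 4.1% of the SAF. Among those measured it is between 1/63 = 1.6% and 5/30 = 16.7%.

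**6. Change from baseline.** For ACT it stays at 0 throughout, because new cases have no baseline and drop out. For PEF it also stays at 0 when nobody changes, since each subject is compared with their own baseline. However, the set averaged still differs by visit.

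**7. With a fixed cohort** (asthma history only for ACT; PEF shown separately by history), the shifts in steps 2 to 5 are all 0.

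**The case against.** The case against has several sound parts.

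- **Asthma safety does not rest on these tables.** New or worsening asthma is an AESI (Protocol 13.1.1), an independent committee reviews all asthma-related AEs (Protocol 15.2), and the SAP plans AESI, adjudicated-event and asthma-specific tables and listings. This stands. A reader might infer that the plan leaves the asthma question unanswered; it does not.
- **Change from baseline already does part of the work.** This also stands. For ACT it is limited to subjects with a pre-dose score, and for PEF at Visits 3 and 5 it uses each asthmatic subject's own baseline. A reader might infer that every trend in these tables is artificial. Only the observed-value rows and threshold counts are affected.
- **The PEF switch is the same in both arms.** The schedule does not depend on arm, and assignment is randomised. Apart from de novo entrants, there is no expected between-arm bias at a given visit. The distortion is over time.
- **More subjects at ACT ≤ 19 is a genuine signal.** Agreed. The count should be kept, but shown where the reader can see that it comes from new cases.
- **No data are lost.** All ACT and PEF values are listed (SAP 10.8; Listing 16.2.9.5). De novo subjects can still appear in the ≥ 15% drop listing through PEF, for which they have a baseline. Only the ACT part of that listing is closed to them.
- **The n is shown, and table shells are not in the public text.** A fall in n would alert a careful reader, and a subset footnote cannot be ruled out. Neither appears as a rule in the SAP text.

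What remains is that the written plan fixes no cohort and states no split by asthma history.

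**Conclusion.** The point holds for the observed by-visit values and the ACT ≤ 19 and PEF < 80% counts. The PEF cohort change is built into the schedule and makes levels at Visits 3 and 5 non-comparable with the other visits, in both arms alike. The ACT effect arises only if de novo asthma occurs. It affects the comparison between arms only if new cases differ by arm in number, timing or score. ACT change from baseline is not shifted by new entrants, but it leaves them out.

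The size cannot be taken from the documents. The illustrated ranges (2.5 to 12.0 points for PEF, 0 to 1.50 points for ACT) rest entirely on the assumed asthma prevalence, PEF gap, number of new cases and their scores.

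The consequence is supportive safety tables that are easy to misread. The primary and secondary vaccine analyses and the adjudicated asthma reporting are untouched. This is a worthwhile, inexpensive improvement rather than a threat to the trial's conclusions.

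**What to change.** In SAP 10.8.1 and 10.8.3:

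- Present by-visit ACT and PEF by asthma history at baseline.
- Show PEF at Visits 3 and 5 for the asthma-history group only, beside that group's own baseline.
- Put de novo subjects' ACT values and ACT ≤ 19 count on a separate line, so that the signal is kept but not pooled into the by-visit mean. Compare their PEF with their existing PEF baseline.
- State in a table note who is measured at each visit.

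As a minor related point, summarise post-screening height in SAP 10.5 for adolescents only, because the present row moves from all subjects to adolescents.

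The cost is SAP wording and a by-group split of tables already planned. No new data are needed. The drawback is smaller groups in each table.
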